### 6.5.5. Prior and concomitant therapy

Concomitant medications will be coded using the WHO Drug Dictionary.

Concomitant medications are those medications taken on or after the initiation of study drug in C5351005 study. This definition includes medications started prior to the initiation of study drug including parent study but continue concurrently with study drug.

Prior medications are those medications taken prior to the initiation of study drug in the parent study.

Prior and Concomitant medications will be summarized descriptively (Section 5.3).

### 6.5.6. Potential Hy's Law

A listing of potential Hy's Law cases will be provided. Participants with AST or ALT  $\geq 3$ x ULN and Total Bilirubin  $\geq 2$ x ULN will be included in this listing.

### 6.5.7. Weight

Weight (kg) will be listed.

## 7. INTERIM ANALYSES

Not applicable

## 8. REFERENCES

## Appendix 1. Data Derivation Details

### Appendix 1.1. Definition and Use of Visit Windows in Reporting

Below are the analysis visit windows for different endpoints:

**Table 2: Analysis visit windows for participants with delayed start: vital signs**

Analysis Visit Time	Target Study Day	Per Protocol Study Day Range	Study Day Range for Statistical Analysis*
Baseline visit	1	[-29, 31]	[**, 1]
Week 1	7	[4, 10]	[2, 10]
Week 2	14	[11, 17]	[11, 21]
Week 4	28	[25, 31]	[22, 35]
Week 6	42	[39, 45]	[36, 49]
Week 8	56	[53, 59]	[50, 70]
Week 12	84	[77, 91]	[71, 98]
Week 16	112	[105, 119]	[99, 126]
Week 20	140	[133, 147]	[127, 154]
Week 24	168	[161, 175]	[155, 210]
Week 36	252	[238, 266]	[211, 294]
Week 48	336	[322, 350]	[295, 378]
Week 60	420	[406, 434]	[379, 462]
Week 72	504	[490, 518]	[463, 546]
Week 84	588	[574, 602]	[547, 630]
Every 12 weeks	672	[658, 686]	...
.....			

\*If multiple assessments occur within a visit window, then the average of those assessments will be used for summarization and analysis.

\*\* Refer to Appendix 1.2 for baseline derivation rules

**Table 3: Analysis visit windows for participants with delayed start: labs (hematology and chemistry)**

Analysis Visit Time	Target Study Day	Per Protocol Study Day Range	Study Day Range for Statistical Analysis*
Baseline visit	1	[-29, 31]	[**, 1]
Week 2	14	[11, 17]	[2, 21]
Week 4	28	[25, 31]	[22, 35]
Week 6	42	[39, 45]	[36, 49]
Week 8	56	[53, 59]	[50, 70]
Week 12	84	[77, 91]	[71, 98]
Week 16	112	[105, 119]	[99, 126]
Week 20	140	[133, 147]	[127, 154]
Week 24	168	[161, 175]	[155, 210]
Week 36	252	[238, 266]	[211, 294]
Week 48	336	[322, 350]	[295, 378]
Week 60	420	[406, 434]	[379, 462]
Week 72	504	[490, 518]	[463, 546]
Week 84	588	[574, 602]	[547, 630]
Every 12 weeks	672	[658, 686]	...
.....			

\*If multiple assessments occur within a visit window, then the average of those assessments will be used for summarization and analysis.

\*\* Refer to Appendix 1.2 for baseline derivation rules

**Table 4: Analysis visit windows for participants with delayed start: EPO, pharmacodynamic endpoints and PROs**

Analysis Visit Time	Target Study Day	Per Protocol Study Day Range	Study Day Range for Statistical Analysis*
Baseline visit	1	[-29, 31]	[**, 1]
Week 12	84	[77, 91]	[42, 126]
Week 24	168	[161, 175]	[127, 210]
Week 36	252	[238, 266]	[211, 294]
Week 48	336	[322, 350]	[295, 378]
Week 60	420	[406, 434]	[379, 462]
Week 72	504	[490, 518]	[463, 546]
Week 84	588	[574, 602]	[547, 630]
Every 12 weeks	672	[658, 686]	...
.....			

Pharmacodynamic endpoints include RBC deformability, flow adhesion and blood smear.

\*If multiple assessments occur within a visit window, then the average of those assessments will be used for summarization and analysis. For PROs and pharmacodynamic endpoints, if multiple assessments occur within a visit window, the assessment before or on the target study day will be used for summarization and analysis.

\*\* Refer to Appendix 1.2 for baseline derivation rules

**Table 5: Analysis visit windows for participants without delayed start: vital signs, EPO, pharmacodynamic endpoints, PROs, labs (hematology and chemistry)**

Analysis Visit Time	Target Study Day	Per Protocol Study Day Range	Study Day Range for Statistical Analysis*
**Baseline visit	NA	NA	NA
Week 12	84	[77, 91]	[42, 126]
Week 24	168	[161, 175]	[127, 210]
Week 36	252	[238, 266]	[211, 294]
Week 48	336	[322, 350]	[295, 378]
Week 60	420	[406, 434]	[379, 462]
Week 72	504	[490, 518]	[463, 546]
Week 84	588	[574, 589]	[547, 630]
Every 12 weeks	672	[658, 686]	...
...			

Pharmacodynamic endpoints include RBC deformability, flow adhesion and blood smear.

\*If multiple assessments occur within a visit window, then the average of those assessments will be used for summarization and analysis. For PROs and pharmacodynamic endpoints, if multiple assessments occur within a visit window, the assessment before or on the target study day will be used for summarization and analysis.

\*\* This is taken from the Week 12 EOT analysis visit (See Appendix 1.2) from C5351004 parent study.

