**Adult Participants from Part A of C5351004 and Other Applicable Osivelotor Open Label Studies with no Delay of Start**

**Table 2. Schedule of Assessments for Adult Participants from Part A of C5351004 and Other Applicable Osivelotor Open Label Studies with no Delay of Start**

	Treatment Period				
Study Week	Baseline visit	12	24	Every 12 weeks	EOS k /ET
Study Day	1 (± 30)	84 (± 7)	168 (± 7)	252+ (± 14 Days)	
Informed consent/assent	X				
Eligibility assessment	X				
Medical history	X				
Physical examination a	X	X	X	X	X
Height	X				
Weight	X	X	X	X	X
Vital signs b	X	X	X	X	X
Serology (hepatitis A, B, C, HIV) only if clinically indicated	X				
Hematology including reticulocyte count and serum chemistry		X	X	X	X
aPTT, INR, PT	X				
Serum erythropoietin	X	X	X	X	X
eGFR (for adults, children or infants) or eCrCl (adolescents) c	X		X	X	X
Urinalysis	X	X	X	X	X
Pregnancy test (for females, post menarche) d	X	X	X	X	X
Contraception check i	X	X	X	X	X

**Table 2. Schedule of Assessments for Adult Participants from Part A of C5351004 and Other Applicable Osiveltor Open Label Studies with no Delay of Start**

	Treatment Period				
Study Week	Baseline visit	12	24	Every 12 weeks	EOS k /ET
Study Day	1 (± 30)	84 (± 7)	168 (± 7)	252+ (± 14 Days)	
PK samples (whole blood and plasma) e	X	X	X	X	X
RBC deformability and RBC mitochondrial content (at sites where available) f,j	X	X	X	X	X
Flow adhesion f,j	X	X	X	X	X
Peripheral blood smear f,j	X	X	X	X	X
Exploratory Biomarkers 	X	X	X	X	X
PGI-C/CGI-C f	X	X	X	X	X
PGI-S/CGI-S f	X	X	X	X	X
PROMIS SF Fatigue 13a, SF Pain Interference 8a, and NRS Pain Intensity f	X	X	X	X	X
EQ-5D-5L f	X	X	X	X	X
WPAI+CIQ:SCD f	X	X	X	X	X
Qualitative interview f,g	X				
Study drug administration	←-----→				
Dispense study drug	X	X	X	X	
Return unused study drug h		X	X	X	X
Concomitant medication	X	X	X	X	X
Serious and nonserious AE monitoring	X	X	X	X	X

**Table 2. Schedule of Assessments for Adult Participants from Part A of C5351004 and Other Applicable Osiveltor Open Label Studies with no Delay of Start**

	Treatment Period				
Study Week	Baseline visit	12	24	Every 12 weeks	EOS k /ET
Study Day	1 (± 30)	84 (± 7)	168 (± 7)	252+ (± 14 Days)	

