## Clinical Experience

Two Phase 1 clinical studies have been completed.

A first-in-human single ascending and multiple ascending dose (SAD/MAD) study in healthy participants (GBT021601-011) has been completed. Safety and PK data on single doses up to 3000 mg in healthy participants demonstrated that osivelotor was well tolerated with a linear dose-dependent increase in percent Hb occupancy. Absorption following a single oral dose was relatively quick in plasma, with  $T_{max}$  generally ranging 0.5-3 h. Peak concentration in whole blood was achieved slower with  $T_{max}$  generally ranging 8-48 h. The terminal elimination half-life of approximately 25 to 28 days in plasma and blood was observed in healthy volunteers; however, approximately 3-fold lower terminal half-life (approximately 10 days) in plasma and whole blood was observed in SCD patients. PK exposure is generally dose-proportional and displays a high partitioning to whole blood (blood/plasma ratios of ~213 and ~68 for healthy volunteers and SCD patients, respectively, following a single 100 mg dose).

In addition, a Phase 1b Study GBT021601-012 in adult participants with SCD was conducted to evaluate the PK, safety, tolerability, and PD of single dose and MAD of osivelotor. In this open label study, a within participant dose escalation was explored. Safety, tolerability, and available PK data after each dose level were reviewed by the Safety Review Committee before escalation to the next dose level. Six adults with SCD received a single 100 mg dose of osivelotor. After an 8-week washout, participants received osivelotor loading doses of 300 mg on Day 1 and 200 mg on Day 2, followed by a maintenance dose of 50 mg/day for 5 weeks. Dose escalation occurred at Week 13 with participants receiving a 500 mg dose on Day 91, 400 mg dose on Day 92, followed by a maintenance dose of 100 mg/day for approximately 3 weeks. The study was amended to evaluate an additional maintenance dose of 150 mg/day over 6 weeks.

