Participants will be followed for approximately 12 weeks after completing dosing to further assess safety. Participants should return to the study site for an EOS visit approximately 12 weeks after the last dose of study drug.

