### 10.1. Statistical Hypothesis

No formal hypothesis will be assessed.

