#### **10.5. Sample Size Determination**

The sample size is based on the number of participants who will complete the parent studies and consent to continue to this study. Therefore, approximately 500 participants are anticipated to enroll in this long-term follow-up study.

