**2.2.3. Study Design**

C5351005 (OLE) is designed as a multicenter, global, open-label extension study. The primary objective is to assess the long-term safety of osivelotor in participants with SCD. This study is available to eligible participants who have previously enrolled in a Pfizer-sponsored osivelotor clinical study and meet the entry criteria for this study.

Eligible participants will receive open-label osivelotor at Baseline (Day 1). It is intended that Day 1 coincides with the final visit from the originating osivelotor study. End of Treatment (EOT) assessments from the originating study will serve as Baseline assessments for this study. If Day 1 for this study is greater than 7 days from the completion of the originating study, new baseline assessments will be obtained. If during the period between Day 1 of this study and completion of the originating study no dose is received for greater than 3 consecutive days, an appropriate loading dose will be administered prior to continued maintenance dosing.

Only participants from C5351004 Part A (also referred to as the “parent study”) were enrolled into the OLE. C5351004 Part A is a study which enrolled only adult participants. There are two sets of participants rolling over from C5351004 Part A to the OLE study – (i) participants without a delayed start (Date of first dose in C5351005 – EOT date from C5351004 + 1 ≤ 42 days) and (ii) participants with a delayed start of OLE (Date of first dose in C5351005 – EOT date from C5351004 + 1 > 42 days). Each set follows a distinct schedule of assessments as outlined in the C5351005 protocol.

**3. ENDPOINTS AND BASELINE VARIABLES: DEFINITIONS AND CONVENTIONS****3.1. Primary Endpoint(s)****3.1.1. Incidence of TEAEs**

A treatment-emergent adverse event (TEAE) is defined as an AE that occurs during the effective duration of treatment defined as the time from the first dose of study drug through last dose of study drug + 56 days.

TEAEs that occur in the parent study are not counted as TEAEs in this study. In case, the start date of AE is the same date as the treatment start date and the question in the AE CRF page “Is this AE continuing from the parent study?” = “Yes”, then the event is not a TEAE,

as long as it can be confirmed that the AE in question had a start date in the parent study and no end date in the parent study.

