#### **6.2.2. Change from baseline in hematological laboratory parameters, including hemoglobin, reticulocytes, lactate dehydrogenase, and unconjugated bilirubin.**

Descriptive statistics (Section 5.3) for each parameter will be presented at baseline and each evaluation post baseline. Change from baseline for each post baseline evaluation will also be presented.

Mean (SD) for both raw values and change from baseline values will be plotted over time. These figures will be presented for each parameter separately.

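### SAP visit windows have no end-of-study row and no last-dose limit, so washed-out values are reported as Week-X results

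*SAP*

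**What the plan says.** **Timing and content of EOS.** Protocol 5.1 states: "Participants should return to the study site for an EOS visit approximately 12 weeks after the last dose of study drug". SAP 2.2.3 says that only Part A participants entered, so schedule Tables 1 and 2 of the protocol apply. Both mark vital signs, EPO, PROs and the row "Hematology including reticulocyte count and serum chemistry" in the EOS/ET column. SAP Section 2 places the primary analysis after everyone has had EOS or left the study, so these records will be in the data.

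**Windows.** SAP Appendix 1.1, Tables 2 to 5, assigns values to Week 1, 2, 4 and so on by study day counted from first dose. The windows run on without a break. No row is given for EOS or follow-up, and no condition refers to the last dose. Where a window holds several values, labs, vital signs and EPO follow the rule "If multiple assessments occur within a visit window, then the average of those assessments will be used for summarization and analysis". PROs and pharmacodynamic endpoints take the value on or before the target day. Section 5.1 exempts only PK from windowing.

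**Summaries.** SAP 6.2.2 says of the hematology endpoints: "Descriptive statistics (Section 5.3) for each parameter will be presented at baseline and each evaluation post baseline". Sections 6.1.2 and 6.1.3 do the same for other labs and vital signs. Sections 6.2.2 and 6.3.4 plot hematology and EPO means over time.

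**Last-dose limits elsewhere.** SAP 3.1.1 counts TEAEs from first dose "through last dose of study drug + 56 days". SAP 6.2.1 counts VOC person-time to the end-of-treatment date.

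**The concern.** The EOS delay of 12 weeks equals one visit interval of the long-term schedule. A participant whose last dose is on Day 168 has EOS at Day 252, which is the Week 36 target day. The value is then reported as a Week 36 result although dosing stopped 84 days earlier.

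The secondary objective concerns the effect of long-term use on hemolytic anemia. If hemoglobin, reticulocytes, LDH and bilirubin drift back after stopping, a table or plot that mixes these values with on-drug ones would look like an effect fading during treatment. Later windows are the most exposed, because fewer participants remain on drug to balance the EOS values.

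**Working it through.** No sample size or power figure bears on this. The check is of the windows, the drug remaining and the resulting mean.

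**1. Reproduce the plan's windows.** Interior bounds are midpoints of adjacent target days: (168 + 252)/2 = 210 and (252 + 336)/2 = 294, so Week 36 is Days 211 to 294, as printed. Every interior bound in SAP Tables 3 and 5 matches, and the windows are contiguous.

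**2. Where EOS falls.** EOS day = last dose day + 84. Last-dose Days 1 to 546 give EOS Days 85 to 630. All 546 of 546 fall in a labelled Week-X window, in both tables.

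**3. Does EOS share a window with the same participant's on-drug value?** This needs two days 84 apart inside one window. Table 3 windows span at most 84 days, so 0 of 546 last-dose days allow it. In Table 5 only the Week 12 window (Days 42 to 126, 85 days) does: last dose Day 42, EOS Day 126, which is 1 of 546. If EOS comes early, at +77 or +70 days, the counts rise to 50 of 553 and 99 of 560 (Table 5) or 35 of 553 and 70 of 560 (Table 3), but an unscheduled on-drug value would be needed. At +91 days it is 0 of 539 in both. So the EOS value normally stands alone in its window.

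**4. Drug remaining.** Protocol 3.1 reports: "approximately 3-fold lower terminal half-life (approximately 10 days) in plasma and whole blood was observed in SCD patients". Fraction left = 2^(−days/10):
- 42 days: 2^(−4.2) = 5.4%
- 56 days: 2^(−5.6) = 2.1%
- 84 days: 2^(−8.4) = 0.3%

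**5. Shift in the window mean.** With f the off-drug share of values, mean change = (1 − f) × on-drug change + f × off-drug change. For illustration, take a 2.3 g/dL effect (Protocol 3.1: mean rise in six Phase 1b participants) and assume full reversal.

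| f | Off-drug baseline (+2.3 on, 0 off) | On-drug baseline (0 on, −2.3 off) | Shift |
|---|---|---|---|
| 10% | +2.07 | −0.23 | −0.23 |
| 20% | +1.84 | −0.46 | −0.46 |
| 50% | +1.15 | −1.15 | −1.15 |

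SAP Appendix 1.2 decides the column. A gap under 7 days uses the parent study's on-drug Week 12 value. A longer gap uses pre-dose Day 1, which is largely off drug for delayed starters (over 42 days). Gaps of 7 to 42 days lie in between.

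**6. How large could f be?** The documents give no last-dose dates. Assume last-dose days uniform over 84 to 504, all visits on target and all EOS visits attended at +84. In Table 5, counting last-dose days that give an off-drug value over all that give a value:
- Week 24: 43/(337 + 43) = 11%
- Week 36: 84/(253 + 84) = 25%
- Week 48: 84/(169 + 84) = 33%
- Week 60: 84/(85 + 84) = 50%
- Week 72: 84/(1 + 84) = 99%

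The Week 72 figure reflects the assumed ceiling of Day 504. Starting the range at Day 168 gives 0% at Week 24 and 14% at Week 36. Starting it at Day 1 gives 20% and 25%. Week 48 and later hardly change.

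**The case against.** **The SAP never says that EOS visits are windowed.** True: it follows from applying the tables as written. But only PK is exempted by name, and a programmer given these tables has nowhere else to put an EOS lab value. Sections 6.3.2 and 6.3.3 do average smear and deformability records by nominal visit, which sits badly with Tables 4 and 5. That needs reconciling and does not cover labs, vital signs or EPO.

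**The safety estimand takes all data after consent.** This stands for primary labs and vital signs, where off-drug data belong in the analysis. A reader might infer that including them breaches the estimand; it does not. The fault is labelling and mixing. For the hematology endpoints, SAP 2.1 also keeps data after the protocol's intercurrent events, but that list (Protocol 10.3.3) covers new hydroxyurea, prohibited or restricted drugs and transfusion, not stopping study drug.

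**Not every EOS/ET record is washed out.** This stands. Protocol 8.3 asks for a visit at the time of leaving the study, which may be on drug, so the rule must use days since last dose and not the visit name.

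**The hemoglobin figures are illustrative.** This stands. The 2.3 g/dL comes from six participants in another study, full reversal is assumed, and the shares have no source in the documents.

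**The study is descriptive.** Protocol 10.1: "No formal hypothesis will be assessed". No decision rule depends on these tables, which limits the severity.

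**Conclusion.** The concern holds as a reporting defect. Followed as written, the SAP reports values taken about 84 days off drug as Week-X results in the by-visit hematology, lab, vital-sign and EPO tables, the PRO summaries, and the hematology and EPO plots. The direction for hemoglobin is downward in both groups: an understated gain with an off-drug baseline, an apparent decline with an on-drug one. The shift is f × 2.3 g/dL under the assumptions above, and f cannot be fixed from the documents.

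Three stronger readings are tempting and not supported:
- That the averaging footnote blends each participant's on- and off-drug values. Step 3 shows that this almost never happens. The mixing is between participants.
- That dilution describes the whole study. With an on-drug baseline there is no gain in the extension to dilute.
- That safety results in general are affected. TEAE incidence and on-treatment VOC rates have their own last-dose limits and do not use these windows.

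Should-fix, before the tables are programmed.

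**What to change.** In SAP Appendix 1.1, Tables 2 to 5:
- Assign values by days since last dose as well as study day. A value after a stated cut-off goes to a separate row for post-treatment follow-up/EOS, with its own change from baseline, and not to a Week-X window. The SAP's own last dose + 56 days is a natural choice, since it matches the TEAE period. Whatever the choice, it should be stated.
- Let ET visits within the cut-off stay in their Week-X window.
- Keep an all-data summary of labs and vital signs for the primary safety estimand.
- Reconcile the nominal-visit rule of Sections 6.3.2 and 6.3.3 with Tables 4 and 5.

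The cost is SAP wording and one derivation flag, as Section 5.1 already defines the last-dose date. The downside is fewer values in late windows. A 56-day limit would also still admit partly washed-out values from early-termination or unscheduled visits, which should be noted beside the tables.

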## 5. STUDY DESIGN

### 5.1. Overall Design

This multicenter, global, open-label extension study is designed to assess the safety of long-term treatment with osivelotor in participants with SCD. The study will be conducted globally and will be available to eligible participants enrolled in a prior Pfizer-sponsored osivelotor clinical study (originating study). Participants must meet the entry criteria for this

study to be eligible for enrollment (see Section 6.1). The study will have a global distribution, and up to approximately 500 participants will be enrolled.

Eligible participants will receive osivelotor administered orally daily if they continue to receive clinical benefit that outweighs risk, as determined by the Investigator, until the participant has access to osivelotor from an alternative source (eg, through commercialization or a managed-access program).

Eligible participants will receive open-label osivelotor at Baseline (Day 1). It is intended that Day 1 coincides with the final visit from the originating osivelotor study. End of Treatment (EOT) assessments from the originating study will serve as Baseline assessments for this study. If Day 1 for this study is greater than 7 days from the completion of the originating study, new baseline assessments will be obtained. If during the period between Day 1 of this study and completion of the originating study no dose is received for greater than 3 consecutive days, an appropriate loading dose will be administered prior to continued maintenance dosing (see Section 11.3 for detail). Additional assessments that may not have been included in the prior EOT assessments are outlined in the Schedule of Assessments and will need to be completed prior to study drug administration.

Participants who participated in Part A of C5351004 or any other open label osivelotor study, will undergo safety and outcome assessments at Baseline (Day 1) and every 12 weeks thereafter (Table 2).

Participants from Part B of C5351004, or any other randomized, blinded, placebo controlled osivelotor study will undergo safety and outcome assessments at Baseline (Day 1), Week 8, Week 16, Week 24, and every 12 weeks thereafter (Table 3).

Pediatric participants from Part C of C5351004 will undergo safety and outcome assessments at Baseline (Day 1), Week 2, Week 4, Week 8, Week 12, Week 16, Week 20, Week 24, and every 12 weeks thereafter (Table 4).

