### 8.3. Discontinuation/Withdrawal from the Study

- A participant may withdraw from the study at any time at their own request or may be withdrawn at any time at the discretion of the Investigator for safety, behavioral, or compliance reasons.
- At the time of discontinuing from the study, if possible, an early discontinuation visit should be conducted, as shown in the Schedule of Assessments (SoA) Section 2.1. The SoA details the data to be collected at the time of study discontinuation and follow-up and for any further evaluations that need to be completed.
- The participant will be permanently discontinued from the study treatment and the study at that time.
- If the participant/parent/legal guardian/legally authorized representative withdraws consent for disclosure of future information, the Sponsor may retain and continue to use any data collected before such a withdrawal of consent.
- If a participant withdraws from the study, they may request destruction of any samples taken and not tested, and the Investigator must document this in the site study records.

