#### **9.10. Missed Assessments**

Missed assessments should be rescheduled and performed as close to the original scheduled date as possible. An exception is made when rescheduling becomes, in the Investigator's opinion, medically unnecessary or unsafe because it is too close in time to the next scheduled evaluation. In that case, the missed evaluation should be abandoned.

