#### 6.3.2. Change from baseline in RBC sickling from peripheral blood smears.

Descriptive statistics (Section 5.3) will be presented at baseline and each evaluation post baseline. Change from baseline and percent change from baseline for each post baseline evaluation will also be presented.

For baseline, the first available record within the nominal visit (Day 1) will be used. All other records from this nominal visit will not be used in analysis. For post-baseline records, the average of all assessments that belong to same nominal visit will be used.

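### When a window holds a second PD or PRO assessment, the rule in SAP Tables 4 and 5 can leave no qualifying value, leave the choice undefined, or displace an on-time visit

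*SAP*

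**What the plan says.** The SAP groups three endpoints under the footnote to Table 4, which Table 5 repeats: "Pharmacodynamic endpoints include RBC deformability, flow adhesion and blood smear". The default for the endpoints in these tables, which applies to erythropoietin for example, is averaging: "If multiple assessments occur within a visit window, then the average of those assessments will be used for summarization and analysis". PROs and PD endpoints are carved out: "For PROs and pharmacodynamic endpoints, if multiple assessments occur within a visit window", then "the assessment before or on the target study day will be used for summarization and analysis". The footnote does not say what happens if no assessment, or more than one, meets that condition.

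For smear, SAP 6.3.2 adds: "For post-baseline records, the average of all assessments that belong to same nominal visit will be used". SAP 6.3.3 says the same for deformability. SAP 5.1 defines a study visit as the nominal CRF visit, refers windowing to Appendix 1 and exempts only PK.

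According to SAP 2.2.3, only adults from Part A of the parent study were enrolled, so the relevant schedules are Protocol Tables 1 and 2. Both place smear, deformability, flow adhesion and PROs at baseline, Week 12, Week 24, every 12 weeks after that, and EOS/ET. On withdrawal, Protocol 8.3 says that, if possible, "an early discontinuation visit should be conducted, as shown in the Schedule of Assessments (SoA) Section 2.1". It fixes no day for that visit.

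**The concern.** A windowing rule should return exactly one value for every window that contains usable data, and it should favour the visit that best represents the time point. This rule looks only at which side of the target an assessment falls on, not at how far away it is. A visit a few days late but inside its protocol window is used if it is alone. It stops qualifying once a second assessment lands in the same window.

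At stake are the by-visit summaries of smear, deformability, flow adhesion and the PROs. Two programmers could build different datasets from the same records. In an open-label study the gap could also be closed with results in view.

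**Working it through.** **Inputs.** From SAP Table 4: Week 12 has target 84, protocol range 77-91 and analysis window 42-126. Week 24 has 168, 161-175 and 127-210. Week 36 has 252, 238-266 and 211-294. The protocol ranges reproduce as 84 ± 7, 168 ± 7 and 252 ± 14. The plan states no figure for how often the rule would apply.

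**Step 1: windows.** Width = upper - lower + 1: 126 - 42 + 1 = 85 days for Week 12, and 210 - 127 + 1 = 294 - 211 + 1 = 84 days for Weeks 24 and 36. They reach 42, 41 and 41 days before the target, and 42 days after it.

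**Step 2: compliant days after the target.** For ±7-day visits, 7 / 15 = 46.7%. For ±14-day visits, 14 / 29 = 48.3%.

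**Step 3: the rule applied literally, beside a closest-to-target rule.**

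| Window (target) | Assessment days | Footnote | Closest (days from target) |
|---|---|---|---|
| Week 36 (252) | 255, 285 | none qualifies | 255 (3 v 33) |
| Week 24 (168) | 170, 200 | none qualifies | 170 (2 v 32) |
| Week 12 (84) | 60, 80 | both qualify, no choice given | 80 (4 v 24) |
| Week 12 (84) | 45, 86 | 45 | 86 (2 v 39) |
| Week 36 (252) | 250, 285 | 250 | 250 (2 v 33) |
| Week 36 (252) | 242, 257 | 242 | 257 (5 v 10) |

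In the first row, Day 255 alone would be used, because the footnote is not triggered by a single assessment.

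**Step 4: how the outcomes divide.** Pair each on-time day with every other day in the window. This is a count of day pairs, not a probability.

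- Week 12, 15 × 84 = 1,260 pairs: none qualifies 7 × 41 = 287 (22.8%); on-time visit displaced 7 × 43 = 301 (23.9%); two qualify 8 × 42 = 336 (26.7%); on-time visit kept 8 × 42 = 336 (26.7%).
- Week 36, 29 × 83 = 2,407 pairs: 14 × 41 = 574 (23.8%); 14 × 42 = 588 (24.4%); 15 × 41 = 615 (25.6%); 15 × 42 = 630 (26.2%), in the same order.

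**Step 5: the termination route.** Assume that the last scheduled visit is on time and spread evenly over its protocol range, and that a termination visit follows, spread evenly over the next 84 days. The documents give neither distribution. The chance that both fall after the target in one window is the Step 2 share times the mean number of days left in the window, divided by 84.

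- Weeks 12 and 24: 7/15 × 38/84 = 21%, where for Week 12 the mean late day is 88 and 126 - 88 = 38.
- Week 36 onward: 14/29 × 34.5/84 = 20%, where for Week 36 the mean late day is 259.5 and 294 - 259.5 = 34.5.

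**Step 6: the footnote beside 6.3.2 and 6.3.3.** Take two smear records from one Week 12 visit on Day 86. If they are averaged within the nominal visit first, one assessment remains, the footnote is not triggered and the mean is used. If the footnote is applied first, both records are after Day 84 and neither qualifies. The SAP does not state the order.

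**The case against.** The strongest reply is that the trigger is rare by design. These assessments are 12 weeks apart and the windows are 84-85 days wide, so compliant scheduled visits give one assessment per window. Missed assessments do not obviously create duplicates either: "Missed assessments should be rescheduled and performed as close to the original scheduled date as possible", or they are abandoned. This stands, and it limits the size of the problem.

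A reader might infer that an on-time visit is routinely discarded for a much earlier one. The schedules do not support that. No PD or PRO assessment is planned between baseline and Week 12, so Day 45 followed by Day 86 needs an unscheduled assessment. A Week 12 visit that slips into the Week 24 window is on Day 127 or later, at least 127 - 91 = 36 days past its limit. A termination visit cannot be the earlier of the pair, because participation ends there.

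A reader might also infer that participants who leave early often have two assessments in a window and bear most of the loss. That is not shown. Those who stop treatment are asked back about 12 weeks after the last dose, which normally falls in a later window. The route that remains is withdrawal from the study, with a discontinuation visit held if possible on no fixed day. It is realistic but of unknown frequency.

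Finally, Sections 6.3.2 and 6.3.3 might be read as contradicting the footnote. They work within a nominal visit and the footnote works across a window, so averaging first makes them compatible. What remains is that the SAP does not state this order. Flow adhesion and PROs have no second rule.

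**Conclusion.** The point holds as a defect in a stated rule, not merely as missing detail. A valid scheduled value that would be used alone ceases to qualify when a later assessment falls in the same window and both are after the target. Two assessments on or before the target leave the choice undefined. An off-schedule early assessment would displace an on-time visit just after the target. No other part of the SAP supplies a fallback or tie-break. Appendix 1.2 says baseline is set to missing where that is intended, but the footnote says nothing comparable, so the handling of a window with no qualifying value is itself undefined.

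The 47-48% is the share of compliant days after the target. It is not the share of windows affected, and nearly half of all windows should not be inferred to lose their value. The 20-21% in Step 5 applies only to participants with a termination visit and rests on the assumptions stated there. How many windows hold a second assessment cannot be estimated from the documents.

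The affected endpoints are exploratory and summarised descriptively without hypothesis tests. Primary and secondary endpoints do not use this rule. The change is worth making because it is cheap, not because a main conclusion depends on it.

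**What to change.** Replace the PRO and PD part of the footnote to Tables 4 and 5 with two steps. First, average smear and deformability replicates within the nominal visit, as in 6.3.2 and 6.3.3, and do not average PRO responses. Second, if more than one assessment remains in a window, use the one closest to the target study day, or the earlier if they are equidistant.

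PRO responses should stay out of the averaging because SAP 6.3.5 tabulates PGI-S, CGI-S and the EQ-5D-5L dimensions by category, and a mean can fall between categories.

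The cost is about two sentences and a small programming change, with no new data. There is one small downside: a termination visit nearer the target can occasionally replace an on-time scheduled visit, as with Days 242 and 257 in the Week 36 window. If data have already been reviewed, date and document the change.
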